7.2.2 Hypothesis

The hypothesis to be evaluated for the analyses of ORR is as follows:

 H_0 : (Proportion with objective response)_{60mg} = (Proportion with objective response)_{140mg}

 H_a : (Proportion with objective response)_{60mg} \neq (Proportion with objective response)_{140mg}

7.2.3 Primary Analysis

The key analysis of ORR will be based upon evaluations by the IRC and will include all subjects in the ITT population.

The following rules will be followed in determining the date of the objective response:

- If multiple assessment dates are associated with a tumor assessment visit with an overall response of CR or PR, the latest assessment date within the set will be chosen as the response date
- Single missing or not adequate scheduled tumor assessments will be ignored. No values will be imputed

- If missing/inadequate visits are immediately followed by progression or death, only evaluations before the missing/inadequate data will be considered in the determination of BOR
- If the missing/inadequate visits are immediately followed by an adequate assessment with an overall response of SD, PR or CR this will be deemed sufficient clinical evidence that progression did not occur during the period of missing data and the missing evaluations will be ignored. No values will be imputed

If the null hypothesis for the primary PFS analysis is rejected, then ORR between the two treatment groups will be compared using an unstratified two-sided chi-squared test at 5% level of significance. If a sufficient number of responders are observed, analysis using the Cochran-Mantel-Haenszel method to adjust for the stratification factors (see Section 2.4) will be generated.

Point estimates of ORR for each treatment arm, the difference in ORR between the two treatment arms, and associated confidence intervals will be provided. The odds ratio and its confidence intervals will also be shown. The 95% CIs for the point estimate will be calculated using exact methods. The 95% CIs for the difference in ORR between the two treatment arms and for the odds ratio will be calculated by asymptotic methods.

To provide a more detailed understanding of anti-tumor activity, baseline sum of target lesion diameter per IRC, the maximum tumor reduction since baseline in target lesions will be derived for those subjects who have baseline and at least one post-baseline measure. The maximum percent tumor reduction from baseline in target lesions for each arm will be displayed graphically using waterfall plots. For each subject, data from time points after the first date of any of the censoring events defined for the primary analysis of PFS as described in Section 7.1.3 will be excluded from the waterfall plots.

A summary of the concordance between investigator and IRC determined objective response rate will also be provided.

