## 1.4.3.2.2 Efficacy Results for the Phase 3 Study XL184-301

The primary analysis for XL184-301 demonstrated a statistically significant improvement in PFS (p<0.0001) with median PFS of 11.2 months for the cabozantinib arm versus 4.0 months for placebo (hazard ratio [HR], 0.28; 95% confidence interval [CI], 0.19 to 0.40), an estimated 31.2-week (7.2-month) difference in the medians (Figure 1-1; Elisei et al 2013). The Kaplan-Meier estimates of subjects alive and progression-free at 1 year were 47.3% for the cabozantinib arm and 7.2% for placebo.

Figure 1-1: Kaplan-Meier Plot of Progression-Free Survival through the Date of the 138th event, IRC Determination (ITT Population)

The PFS subgroup analysis showed a consistent HR (HR < 1) across pre-specified demographic and baseline disease characteristics including *RET* mutational status (including M918T), prior anticancer or radiotherapy, and prior TKI exposure.

Specifically, for subjects with the RET M918T mutation in their tumor (n=126) the PFS subgroup analysis showed a median PFS of 61 weeks on the cabozantinib arm compared to 17 weeks on the placebo arm (HR, 0.15; 95% CI, 0.08, 0.28; p < 0.0001); in comparison, the HR for the overall ITT population was 0.28 (95% CI: 0.19, 0.40). In addition, the PFS subgroup analysis demonstrated the negative prognostic effect of M918T: on the placebo arm, subjects with M918T had a shorter PFS (17 weeks) compared to subjects with wild-type RET (23 weeks) or RET mutations other than M918T (24 weeks) (Sherman 2013).

The secondary endpoint of ORR also demonstrated a treatment benefit of cabozantinib. In the primary analysis of ORR as determined by the IRC, subjects in the cabozantinib treatment arm had an ORR of 27.9% (all were confirmed PRs) versus 0% for subjects in the placebo arm (p-value <0.0001; stratified Cochran-Mantel-Haenszel test). Responses were durable: the median duration of response was 63.7 weeks (95% CI: 48.14, 76.14) (14.6 months [95% CI: 11.1, 17.5]).

A pre-specified interim analysis of OS was conducted at the time of the primary analysis of PFS when 44% of the 217 required deaths for the final analysis had occurred; there was no observed difference between treatment arms in this interim OS analysis. A subsequent administrative OS

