# **9.2.1.2 Analysis**

The primary efficacy analysis of PFS will include all subjects in the ITT population and will evaluate whether PFS in subjects in the 60 mg cabozantinib arm is non-inferior to subjects in the 140 mg cabozantinib arm. It will include radiographic progression (rPD) events per RECIST 1.1 as determined by the IRC and deaths. The primary efficacy analysis is event based and will be conducted when at least 150 PFS events have been observed.

The following censoring rules will be applied:

- Subjects receiving subsequent anti-cancer therapy (other than palliative bone radiation) before rPD per IRC will be censored at the date of their most recent post-randomization adequate tumor assessment prior to receipt of such therapy
- Subjects who miss two or more scheduled adequate tumor assessments before rPD or death will be censored at the date of their most recent post-randomization adequate tumor assessment prior to the missed assessments
- Subjects who have not progressed or expired as of the date of the analysis data cutoff will
  be censored at the date of their most recent post-randomization adequate tumor
  assessment prior to the data cutoff date
- Censored subjects without an appropriate post-randomization adequate tumor assessment will be censored at the date of randomization

Radiographic assessments are to continue if treatment is discontinued for reasons other than rPD, per the ITT principle such subjects will not necessarily be censored.

Sensitivity analyses with alternative definitions and censoring rules will be defined in the SAP to demonstrate the robustness of the treatment effect and explore the impact of potentially informative censoring.

The median duration of PFS and its associated confidence interval (CI) will be estimated using the Kaplan-Meier product-limit method. The hazard ratio (HR) and the associated 95% CI will be estimated using a Cox proportional- hazards model with treatment group as the independent variable and stratified by the factors that were used for randomization.

Non-inferiority will be concluded if the upper 95% CI for the HR is less than the non-inferiority margin of 1.58.

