2.5 Randomization and Blinding

Study treatment assignment will be unknown to the subjects, investigators, study centers, the sponsor, and any contract research organization affiliated with the study other than those authorized to access treatment assignment for regulatory safety reporting and submission processes, interactive voice recognition/interactive web response system (IVRS/IWRS) administration and drug supply management (see protocol section: Blinding of Study Treatments).

Cabozantinib-matched placebo will be packaged and color-, size-, and shape-matched to be indistinguishable (including imprint on capsules) from cabozantinib.

Randomization will be stratified by the following factor:

• RET M918T status (positive vs negative vs unknown)

The M918T-unknown stratum will contain at most 10% of the total number of enrolled subjects and will be limited to subjects who undergo a tumor biopsy for the purpose of enrolling in the

study but the sequencing analysis of the tumor sample for the RET or RAS mutation status fails, a replacement sample is not available, and an additional biopsy procedure is not feasible.

The randomization scheme employs a permuted block design to help ensure a 1:1 ratio of assignment to the cabozantinib 60 mg or 140 mg groups for the overall population as well as within each level of the stratification factor. Subjects are defined to be enrolled in the study if they are randomized.

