7.6 Subgroup Analyses

Descriptive subgroup statistics will be provided for both PFS and ORR primary analyses, for the following subgroups:

- RET M918T mutation status at randomization per IxRS (positive, negative, unknown)
- RET M918T mutation status at randomization per CRF (positive, negative, unknown)
- Age category 1 (<65 years,≥65 years)
- Age category 2 (<45 years, 45 to <65 years, 65 to <75 years, 75 to <85 years, ≥85 years)

- Sex (Male, Female)
- Race category (White, Non-White, Not Reported)
- ECOG PS (0, 1)
- Geographic region (Europe, Rest of the World)
- Prior systemic non-radiation anti-cancer therapy (Yes, No) for MTC
- Number of prior systemic non-radiation anti-cancer therapy received for MTC $(0,1,2,\geq 3)$
- Prior radiation therapy (Yes, No)

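### Minor: the ORR test that carries alpha ignores the M918T strata used in randomization; a stratified CMH test would be slightly more powerful at almost no cost

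*SAP*

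**What the plan says.** - SAP 2.5 names RET M918T status (positive, negative, unknown) as the only stratification factor. It says "The randomization scheme employs a permuted block design to help ensure a 1:1 ratio of assignment", both overall and within each level of that factor.
- SAP 7.2.3 states that, once the PFS null hypothesis is rejected, the two arms' ORRs are "compared using an unstratified two-sided chi-squared test at 5% level of significance". SAP 7.4 gives this test alpha = 0.05, second in the hierarchy. The protocol synopsis and Protocol 9.2.2.2 also name a two-sided chi-squared test and do not mention strata.
- The stratified analysis is secondary and conditional: "If a sufficient number of responders are observed, analysis using the Cochran-Mantel-Haenszel method" "to adjust for the stratification factors (see Section 2.4) will be generated". No threshold is given, and the section does not say whether M918T is taken from IxRS or CRF.
- Elsewhere the strata are used. The Cox model for PFS in Protocol 9.2.1.2 is "stratified by the factors that were used for randomization". Protocol 1.4.3.2.2 reports the prior Phase 3 ORR of 27.9% "versus 0% for subjects in the placebo arm (p-value <0.0001; stratified Cochran-Mantel-Haenszel test").
- SAP 7.6 plans descriptive ORR by "RET M918T mutation status at randomization per IxRS (positive, negative, unknown") and by the CRF version.

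**The concern.** When arms are balanced within strata by design and the outcome differs between strata, part of the outcome variance cannot contribute to the difference between arms. The pooled variance in the unstratified chi-squared still counts it. The test then rejects less often than 5% under the null and loses power that a stratified test would recover.

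Protocol 1.5.4 gives a qualitative reason to expect an association: it reports trends in response rate by RET genotype. It gives no ORR by M918T stratum.

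The undefined responder condition also leaves open, until the data are seen, whether the adjusted result will be produced at all.

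**Working it through.** **The plan's own figure.** The only power statement is for PFS (SAP 2.3). Events = 4(1.96 + 0.8416)²/(ln 1.58)² = 31.40/0.2092 = 150.05, which rounds up to 151. With the unrounded margin 1.5811 it is 150. Power at 150 events is 80.0%, so the stated figure reproduces. No power is stated for ORR.

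**Inputs.**
- 94 per arm (SAP 2.3).
- M918T-positive share 38% in the prior study (Protocol 1.5.4): 0.38 × 94 = 36.
- Unknown stratum at most 10% (SAP 2.5): 9 per arm. This leaves 49 negative.
- 140 mg ORR 27.9% (Protocol 1.4.3.2.2), also used for the unknown stratum.
- Assumed, because the documents do not give them: positive-minus-negative ORR gap d of 0 to 40 points, the 60 mg ORR, and the block size.

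Holding the overall ORR at 27.9%, the negative-stratum ORR is 27.9% − (36/85)d. Positive/negative ORRs at d = 10/20/30/40 are 33.7/23.7, 39.4/19.4, 45.2/15.2 and 51.0/11.0%.

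**Same numerator, different variance.** Let stratum i have m_i responders in total, x_i of them on 60 mg, and let a and b be the responder totals by arm. With 1:1 balance in each stratum the CMH numerator is Σ(x_i − m_i/2) = (a − b)/2. The unstratified numerator is a − (a + b)/2 = (a − b)/2. So CMH addresses the overall difference in SAP 7.2.2 ("The hypothesis to be evaluated for the analyses of ORR is as follows"), and only the variance changes.

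**Closed form for size.** Let f be the between-stratum share of the response variance. The chi-squared size is 2[1 − Φ(1.96/√(1 − f))]. With shares 38/52/10%, f = 0/0.0109/0.0437/0.0982/0.1746 at d = 0/10/20/30/40. The size is then 5.0/4.9/4.5/3.9/3.1%.

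**Simulation, exact within-stratum balance** (400,000 trials per scenario, no continuity correction). Power is at 60 mg ORR 15% with a common odds ratio.

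| Gap (points) | Chi-squared size | CMH size | Chi-squared power | CMH power | Gain (points) |
|---|---|---|---|---|---|
| 0 | 5.0% | 5.0% | 58.4% | 58.5% | 0.1 |
| 10 | 4.8% | 5.0% | 58.3% | 58.6% | 0.3 |
| 20 | 4.4% | 5.0% | 58.5% | 59.8% | 1.3 |
| 30 | 3.8% | 5.0% | 58.6% | 61.7% | 3.2 |
| 40 | 3.1% | 5.0% | 58.9% | 64.8% | 5.8 |

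Gains were taken before rounding. Chi-squared power does not fall here; the test forgoes the gain.

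**Where the effect lies matters.**
- Effect only in negatives, 60 mg ORR 20%, gaps 0/10/20/30: gain 0.3/1.1/3.0/5.9 points. The last case is extreme: the deficit among negatives is 7.9 × 94/49 = 15.2 points from an ORR of 15.2%, so almost no responders remain.
- Effect only in positives, 60 mg ORR 15%, gaps 20/30/40: gain 0.2/0.9/2.9 points.

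**Permuted blocks of 4, 6 or 8 with random stratum sizes** (300,000 trials per scenario). Chi-squared size is about 5.0/4.9/4.5/3.9/3.1%. The common-odds-ratio gain at 15% is about −0.2/0.1/1.2/3.0/5.7 points.

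A separate simulation with blocks of 4 and a fixed odds ratio of 0.36 gave chi-squared power 78.1/77.6/75.9/73.0/68.4% and CMH 77.9/77.7/76.8/75.4/73.4%. At N = 250 and odds ratio 0.45 the gain is 1.3 points at gap 20 and 3.1 at gap 30.

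**Sparse stratum.** A stratum with no responders adds zero to both the CMH numerator and its variance. The chance of this in an unknown stratum of 18 is 0.721¹⁸ ≈ 0.3%.

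**The case against.** The strongest reply is that this is a choice between two valid, pre-specified tests of a secondary endpoint. The chi-squared tests the marginal hypothesis in SAP 7.2.2 directly, and synopsis, protocol and SAP agree on it. CMH is already planned as an extra, ORR by M918T appears in SAP 7.6, and SAP Table 2 says efficacy analyses will be shown by IxRS and CRF stratification. All of that is true, but none of it gives alpha to the stratified test.

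The gain is also small and conditional. Below a 20-point gap it is negligible. ORR is tested only after PFS non-inferiority, so the powers above are conditional on passing that test. PFS power is 80% at a true HR of 1. At an assumed HR of 1.2 it is Φ((ln 1.58 − ln 1.2)√150/2 − 1.96) = Φ(−0.275) ≈ 39.2%. If PFS and ORR were independent (an assumption), the 3.2-point gain becomes 3.2 × 0.80 ≈ 2.6 or 3.2 × 0.392 ≈ 1.3 points. This stands as a qualification of size.

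The change is not wholly free. CMH loses 0.2-0.3 points under permuted blocks when there is no gap. A SAP-only change also makes the SAP differ from the protocol text.

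The two comparisons are weaker than they look. The strata of the prior study's CMH test are not named, and RET status was defined in only 65% of its subjects. SAP 7.1.3 estimates both stratified and unstratified hazard ratios for PFS. The case therefore rests on the blocking in this trial and not on precedent.

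**Conclusion.** The point holds as a minor, nearly costless improvement and not as an error. Under stratified blocking the unstratified chi-squared is valid but conservative when response differs by M918T status. Its size falls from 5.0% at no gap to 3.1% at a 40-point gap, while CMH stays at about 5.0%.

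The power forgone is nil to 0.3 points for gaps up to 10, about 1 point at 20, 3 at 30 and 6 at 40 under a common odds ratio. It is less if the effect is confined to positives. These figures are conditional on passing the PFS test. They also rest on an assumed M918T gap, assumed 60 mg ORRs and stratum shares carried over from the prior study. The only power loss seen for CMH is 0.2-0.3 points when M918T is unrelated to response.

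**What to change.** In a revised SAP, before unblinded analyses (the route in SAP 4.8):

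1. In SAP 7.2.3, make the two-sided CMH test stratified by M918T status per IxRS the alpha-controlled ORR test, and remove the condition on the number of responders.
2. Keep the unstratified chi-squared as a sensitivity analysis.
3. Add a Mantel-Haenszel risk difference with 95% CI beside the planned unstratified difference and odds ratio, replacing neither. For a common odds ratio at 60 mg ORR 15%, its CI is narrower by 0/0.4/1.8/3.9/6.9% across the five gaps. With a positives-only effect it can be up to 2.4% wider.
4. Record the change from Protocol 9.2.2.2.
5. As a clerical correction, point the cross-reference in SAP 7.2.3 to Section 2.5 instead of 2.4.

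The cost is a SAP revision, with no new data, subjects or visits. Editing the protocol or synopsis to match is optional and would bring IRB/EC submission and approval under Protocol 14.

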7.3 Additional Endpoints

Additional endpoints are listed in Section 2.2.3.

Safety and tolerability as assessed by:

Dose modifications are addressed in Section 6.6

- Adverse events are addressed in Section 8.1
- Changes in laboratory parameters are addressed in Section 8.5

Blood serum samples for the analysis of calcitonin (CTN) and carcinoembryonic antigen (CEA) levels by central lab will be summarized in the ITT population in SI units. Continuous CTN and CEA laboratory test results will be summarized by treatment group using descriptive statistics for actual values and for changes from baseline by scheduled visit. The maximum percent of CTN and CEA laboratory test result reduction from baseline for each arm will be displayed graphically using waterfall plots. Endpoints related to pharmacodynamics and pharmacokinetics listed in Section 2.2.3 (b) - (e) are outside the scope of this plan and will be described in their respective plans.

7.4 Control of Type I Error

The multiplicity issue resulting from analysis of one primary endpoint of PFS and one secondary endpoint of ORR will be addressed by hierarchical testing procedures.

The primary analysis of PFS is event driven and will be conducted after at least 150 events are observed. The hypothesis for PFS will be tested at the two-sided 0.05 level of significance (α). If this hypothesis is rejected then the hypothesis for the secondary endpoint will be tested at α =0.05.

Statistical evaluation of all other endpoints will be considered exploratory.

7.5 Interim Analyses

No interim analyses are planned for this study.

7.6 Subgroup Analyses

Descriptive subgroup statistics will be provided for both PFS and ORR primary analyses, for the following subgroups:

- RET M918T mutation status at randomization per IxRS (positive, negative, unknown)
- RET M918T mutation status at randomization per CRF (positive, negative, unknown)
- Age category 1 (<65 years,≥65 years)
- Age category 2 (<45 years, 45 to <65 years, 65 to <75 years, 75 to <85 years, ≥85 years)

- Sex (Male, Female)
- Race category (White, Non-White, Not Reported)
- ECOG PS (0, 1)
- Geographic region (Europe, Rest of the World)
- Prior systemic non-radiation anti-cancer therapy (Yes, No) for MTC
- Number of prior systemic non-radiation anti-cancer therapy received for MTC $(0,1,2,\geq 3)$
- Prior radiation therapy (Yes, No)

8 SAFETY SUMMARIES

All safety analyses will be performed using all subjects in the Safety population. Any statistical comparisons between the two treatment arms will be considered exploratory.

Safety and tolerability will be assessed by the incidence of treatment emergent-adverse events (TEAEs), changes in laboratory parameters and vital signs from baseline, and ECOG Performance Status.

An Independent Data Monitoring Committee (IDMC) will monitor safety during the study on a regular basis. The committee will operate independently from Exelixis and the clinical investigators.

The primary responsibility of the IDMC is to review the accumulating safety data on a regular and an ad hoc basis and make recommendations to Exelixis regarding the continued conduct of the study. Safety data will be provided at regular intervals to the IDMC in the form of summary reports or data listings from the Sponsor (blinded) or its designated representative (unblinded).

Details regarding IDMC membership, schedule and format of meetings, format for presentation of data, access to interim data, method and timing of providing interim reports to the IDMC, and other issues relevant to committee operations are described in the IDMC charter.

The IDMC members will use their expertise, experience, and judgment to evaluate the safety data from the trial and to recommend to the Sponsor whether the trial should continue or be stopped early for safety. No formal statistical rules recommending early stopping for safety are planned.

8.1 Adverse Events

Adverse event terms recorded on the CRF will be mapped to preferred terms (PTs) and system organ class (SOC) using the Medical Dictionary for Regulatory Activities (MedDRA). The severity of AEs will be evaluated by the investigator per CTCAE v4.0 (Cancer Terminology Criteria for Adverse Events) guidelines. The investigator will also judge each event to be "not related" or "related" to study treatment.

A TEAE is defined as any AE with an onset date on or after the date of the first dose of study treatment or any ongoing event on the date of the first dose of study treatment that worsens in severity after the date of the first dose of study treatment.

The end of the AE observation period is defined as the earliest of 30 days after the date of the decision to permanently discontinue study treatment, date of death, consent withdrawal date, data cutoff date and lost to follow up date.

For the purpose of calculating treatment emergence and inclusion in summary tables, incomplete onset dates will be imputed as detailed in Appendix A.

For AE reporting, percentages $\geq 10\%$ will generally be presented as integers, those < 10% will be presented with 1 decimal place (e.g. X.X%). Rounding rules are provided in Appendix B. Calculations based upon percentages will be based upon original unrounded values.

Overview of AE

An overall summary of TEAEs through end of AE observation period (unless indicated otherwise) will be provided with the number and percent of subjects who experienced the following in each treatment group:

- Subjects with a TEAE
- Subjects with a Related TEAE
- Subjects with a Serious TEAE
- Subjects with a Serious Related TEAE at any time
- Subjects with a Worst Grade 3 or 4 TEAE
- Subjects with a Worst Grade 3 or 4 Related TEAE
- Subjects with a Worst Grade 4 TEAE

- Subjects with a Worst Grade 4 Related TEAE
- Subjects with a Grade 5 TEAE on or after first dose date
- Subjects with a Grade 5 TEAE
 - o Subjects with a Grade 5 TEAE \leq 30 days after the last dose of the study treatment
 - Subjects with a Grade 5 AE judged not to be causally related to PD that occurred ≤
 30 days after last dose of the study treatment
 - o Subjects with a Grade 5 AE >30 days after the last dose of the study treatment
 - Subjects with a Grade 5 AE judged not to be causally related to PD that occurred >30 days after last dose of the study treatment
- Subjects with a Related Grade 5 TEAE at any time
- Subjects with a Related Grade 5 TEAE
- Death at any time
- Subjects who died ≤ 30 days after date of last dose of study treatment
- Subjects who died > 30 days after date of last dose of study treatment
- Subjects with a TEAE leading to Dose Modification
- Subjects with a TEAE leading to Dose Reduction
- Subjects with a TEAE leading to Dose Hold
- Subjects with TEAE leading to Treatment Discontinuation
 - TEAEs not related to disease progression
 - TEAEs related to disease progression

The following summaries of AEs will be provided:

Table 4: Adverse Event Summaries

TEAE included	Row-levels (sorted by)	Columns		
Subject Incidence by SOC, Preferred Term and Severity				
All	SOC and PT (SOC per MedDRA standard, PT within SOC by descending frequency)	Worst severity: Any Grades, Grade 3-4, Grade 4, Grade 5		
Related	SOC and PT (SOC per MedDRA standard, PT within SOC by descending frequency)	Worst severity: Any Grades, Grade 3-4, Grade 4, Grade 5		
Serious	SOC and PT (SOC per MedDRA standard, PT within SOC	Worst severity: Any Grades, Grade 3-4, Grade 4, Grade 5		

TEAE included	Row-levels (sorted by)	Columns
	by descending frequency)	
Related Serious	SOC and PT	Worst severity:
	(SOC per MedDRA standard, PT within SOC by descending frequency)	Any Grades, Grade 3-4, Grade 4, Grade 5
	Subject Incidence by Preferred Term and	l Severity
All	PT	Worst severity:
	(descending frequency of Any Grade)	Any Grades, Grade 3-4, Grade 4, Grade 5
All	PT	Worst severity:
All	(descending frequency of Grade 3-4) PT	Any Grades, Grade 3-4, Grade 4, Grade 5 Worst Severity:
7 H	(descending frequency of Any Grade)	Any Grades, Grade 1, Grade 2, Grade 3, Grade 4,
		Grade 5
Related	PT (1 C C C C C C C C C C C C C C C C C C	Worst severity:
Related	(descending frequency of Any Grade) PT	Any Grades, Grade 3-4, Grade 4, Grade 5 Worst severity:
Related	(descending frequency of Grade 3-4)	Any Grades, Grade 3-4, Grade 4, Grade 5
Serious	PT	Worst severity:
	(descending frequency of Any Grade)	Any Grades, Grade 3-4, Grade 4, Grade 5
Related Serious	PT (descending frequency of Any Grade)	Worst severity: Any Grades, Grade 3-4, Grade 4, Grade 5
Leading to dose reduction	PT (descending frequency of Any Grade)	Worst severity:
Zenamg to deservenent	(descending frequency of Any Grade)	Any Grades, Grade 3-4, Grade 4, Grade 5
Leading to dose reduction	PT	Worst severity:
Y 12 4 1 1 1 1	(descending frequency of Grade 3-4) PT	Any Grades, Grade 3-4, Grade 4, Grade 5
